
| | |
|-----------------------------|--|
| | 
• Be off IV steroids for 24 hours prior to discharge• A steroid prescription, or have completed a 5-day course while admitted• An antibiotic prescribed or have completed a 5-day course while admitted• A scheduled appointment with a care provider within 5 days of discharge• Received COPD education during discharge |
| Statistical Analysis | Analyses is among patients identified as having an acute exacerbation of COPD based on final billed coding. Comparisons of patients hospitalized during the intervention and usual care periods will be made using generalized estimating equations to control for clustering within hospital and repeated measures within hospital. The primary outcome, 60-day utilization, will be compared between the two groups of patients using a logit link in the generalized estimating equations. Results will be presented with odds ratios and 95% confidence intervals. |
| Sample Size Analysis | 8 hospitals will be randomized to intervention in 2 facilities per 2 month increments. With the assumption of detecting a change in rates of 60-day non-elective acute care utilization from 43% in the control period to 33% in the intervention period, 59 patients with COPD exacerbation per hospital per two months is needed to achieve a power of 0.80 (intra-class correlation coefficients (ICC)=0.05 and two-side $\alpha=0.05$). To account for this varying cluster size, we inflated the number of patients by 25% resulting in an average of 74 patients per hospital per two months, resulting in a total sample size of 2960 patients among the intervention group. |

LIST OF ABBREVIATIONS

| | |
|------|---------------------------------------|
| AE | Adverse Event or Acute Exacerbation |
| CHS | Carolinas Healthcare System |
| COPD | Chronic Obstructive Pulmonary Disease |
| EHR | Electronic Health Record |
| ED | Emergency Department |
| PHI | Private Health Information |
| PI | Principal Investigator |
| qid | 4 times per day |

TABLE OF CONTENTS

| | |
|--|------------------------------|
| 1. OBJECTIVES | ERROR! BOOKMARK NOT DEFINED. |
| 1.1. Hypothesis | 10 |
| 1.2. Primary Objective | 10 |
| 1.3. Secondary Objectives | 10 |
| 2. BACKGROUND | 10 |
| 3. RATIONALE | 10 |
| 4. SUBJECT AND SITE SELECTION | 11 |
| 4.1. Accrual..... | 11 |
| 4.2. Subjects..... | 11 |
| 4.3. Participating Sites..... | 12 |
| 4.4. Inclusion/Exclusion Criteria | 12 |
| 4.5. Evaluable Population..... | 13 |

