1.3. Secondary Objectives

- a. The secondary objectives are to examine the COPD clinical pathway's effect on additional patient outcomes, such as the
 - i. CHS Quality, Comfort, and Care 30-day readmission rate. This is a readmission rate among patients with an inpatient readmission to the same CHS facility as the index encounter.
 - ii. The patient-centric 30-day readmission rate. This is a readmission rate among patients with an inpatient or observation readmission to any CHS facility.
- b. The methodology for identification of COPD exacerbation within the first 24 hours of hospital admission will be compared to retrospective identification through billing codes.
- c. Demographics and comorbid conditions will be characterized among the historical population of patients at CHS with COPD exacerbation.

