4. SUBJECT AND SITE SELECTION

4.1 Accrual

A daily patient list will be generated through an automated process utilizing clinical and patient registration information. The list will indicate patients newly hospitalized (hospitalization within the preceding 24-hour period) with symptoms of suspected acute COPD exacerbation, at any of the eight facilities. The list contains inpatient and observation encounters. The patient list will identify patients at any of the eight facilities throughout the project, not just once the facility has implemented the standardized use of the COPD clinical pathway. For the purposes of this project, we are not enrolling towards a targeted patient accrual. We will enroll patients during a pre-determined data collection period, See Section 6.

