4.2 Subjects

An acute exacerbation is defined as an encounter where one the following criteria are met within 24 hours of admission.

- The use of the COPD PowerPlan **or**
- A respiratory therapy navigator notification of COPD exacerbation **or**

- The use of the respiratory therapy department COPD bronchodilator protocol **or**
- A historical diagnosis of COPD **or**
 - A history of COPD in the admitting documentation **or**
 - A COPD diagnosis on the problem list **AND**
 - An order of systemic steroids (prednisone or methylprednisolone)

To identify appropriate records of available clinical data for baseline and historical data collection and analysis, we will provision using the following ICD10 code for COPD: J44.1

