5.2.2 Randomization and allocation

The stepped wedge design implies a baseline period, in which no clusters are exposed to the intervention¹². Then, at the chosen time interval of two months, two hospitals will be randomized to cross from the control to intervention (**Figure 1**). This process continues until all eight hospitals have crossed over to the intervention. The order of this cross over process will be randomized. We will use block randomization to assign two hospitals at a time to switch from the control to intervention using SAS Enterprise Guide version 6.1. Allocation will be communicated only to hospital senior leadership initially to prevent contamination. Others including providers at the hospital will learn of allocation in the month preceding roll-out. Patients in included hospitals will be blinded to the intervention or control period.

[figure not shown]
Figure 1. The stepped wedge study design

| | 1-Apr | 1-Jun | 1-Aug | 1-Oct | 1-Dec | |
|-----------|-------|-------|-------|-------|-------|-----------------------------|
| Cluster 1 | 0 | 1 | 1 | 1 | 1 | 0=control 1=intervention |
| Cluster 2 | 0 | 1 | 1 | 1 | 1 | |
| Cluster 3 | 0 | 0 | 1 | 1 | 1 | |
| Cluster 4 | 0 | 0 | 1 | 1 | 1 | |
| Cluster 5 | 0 | 0 | 0 | 1 | 1 | |
| Cluster 6 | 0 | 0 | 0 | 1 | 1 | |
| Cluster 7 | 0 | 0 | 0 | 0 | 1 | |
| Cluster 8 | 0 | 0 | 0 | 0 | 1 | |

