5.2.3 Sample size analysis

Calculations of sample size were based on the primary endpoints of 60-day non-elective acute care utilization. With the assumption of detecting a change in rates of 60-day non-elective acute care utilization from 43% in the control period to 33% in the intervention period, 59 patients with COPD exacerbation per hospital per two months is needed to achieve a power of 0.80 (intra-class correlation coefficients (ICC)=0.05 and two-side $\alpha=0.05$. Holding other parameters constant, the larger ICC is, the higher the power we will obtain (**Figure 2**). With sample sizes per cluster per two months ranging from 30 to 158, our preliminary data shows that the coefficient of variation (CV) of sample size is approximately 0.5. To account for this varying cluster size, we inflated the number of patients by 25% resulting in an average of 74 patients per hospital per two months¹³, resulting in a total sample size of 2960 patients among the intervention group and 5920 patients overall inclusive of our control population. The power was calculated by using the PASS 15¹⁴.

Figure 2. Alternative Sample Size Estimation

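### Section 5.2.3 states totals twice what the design gives: at 74 patients per hospital-period, 2960 is the whole trial, not the intervention group, and 5920 has no basis in Figure 1

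*Combined protocol and SAP*

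**What the plan says.** Section 5.2.3 powers the trial to detect a fall in 60-day utilization "from 43% in the control period to 33% in the intervention period", with an ICC of 0.05 and two-sided alpha of 0.05. It concludes that "59 patients with COPD exacerbation per hospital per two months is needed to achieve a power of 0.80". It then adds 25% for varying cluster size (coefficient of variation about 0.5), which raises the mean cell size to 74, and gives the totals as follows: "resulting in a total sample size of 2960 patients among the intervention group and 5920 patients overall inclusive of our control population".

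The Sample Size Analysis row of the synopsis gives the same derivation and ends "resulting in a total sample size of 2960 patients among the intervention group". It states no overall total.

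Figure 1 in Section 5.2.2 lays out eight hospitals over five two-month periods starting in April. All eight begin in control, and two cross over at each later step. The row for the first hospital to cross reads "Cluster 1 | 0 | 1 | 1 | 1 | 1", with 0 for control and 1 for intervention.

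Two other places bear on how the totals might be read. Section 4.1 says "we are not enrolling towards a targeted patient accrual". Sections 1.3 and 4.2 mention historical patients, the latter in setting out how records will be found: "To identify appropriate records of available clinical data for baseline and historical data collection and analysis".

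**The concern.** In a stepped-wedge trial every hospital contributes both control and intervention periods, so the total is the number of hospital-periods times the average cell size. That product is exactly the 2960 which the plan assigns to the intervention group alone. The plan then gives an overall figure of exactly twice that, as if a control group of equal size had still to be added.

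The planned sample size is a headline figure, and Section 5.2.4 commits to reporting under the CONSORT extension for cluster trials. If the hospitals delivered exactly the average that the plan asks for, the report would show about 1480 intervention patients against a stated 2960, and the trial would look half-enrolled when it had met its requirement. A reader who took the totals at face value would also credit the plan with far more power than its 80% target.

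**Working it through.** **Inputs.** From Section 5.2.3: 43% vs 33%, power 0.80, ICC 0.05, two-sided alpha 0.05, 59 per hospital per two months, inflation 25%, resulting average 74. From Figure 1: 8 hospitals, 5 periods, two hospitals crossing at each of four steps.

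**1. Count the cells in Figure 1.**
- All cells: 8 × 5 = 40.
- Intervention: 2×4 + 2×3 + 2×2 + 2×1 = 20.
- Control: 40 − 20 = 20.

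**2. Reproduce the 59.** The Hussey–Hughes variance for a stepped wedge with I hospitals, T periods and m patients per cell is

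`Var = I·s²·(s² + T·τ²) / [(I·U − W)·s² + (U² + I·T·U − T·W − I·V)·τ²]`

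where U is the number of intervention cells, W the sum of squared column totals and V the sum of squared row totals.

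- Figure 1 gives U = 20, W = 0 + 4 + 16 + 36 + 64 = 120, and V = 2 × (16 + 9 + 4 + 1) = 60.
- So I·U − W = 160 − 120 = 40, and U² + I·T·U − T·W − I·V = 400 + 800 − 600 − 480 = 120.
- With the total variance taken at the control rate, 0.43 × 0.57 = 0.2451: τ² = 0.05 × 0.2451 = 0.01226 and s² = 0.95 × 0.2451 / 59 = 0.003947.
- Var = 8 × 0.003947 × (0.003947 + 5 × 0.01226) / (40 × 0.003947 + 120 × 0.01226) = 0.00206 / 1.628 = 0.001265, so SE = 0.0356.
- Power = Φ(0.10 / 0.0356 − 1.96) = 0.803, and 59 is the smallest cell size that reaches 0.80.

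Taking the variance at the intervention rate, at the mean rate or as the average of the two, and defining the ICC on total or within-cluster variance, gives power of 0.78 to 0.84 at 59 and a required cell size of 53 to 62. The plan's 59 is thus a per-cell figure over all 40 cells, and the control cells are already counted.

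**3. Reproduce the 74.** 59 × (1 + 0.5²) = 59 × 1.25 = 73.75, rounded up to 74.

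**4. Totals at 74 per cell.**

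| | Cells | From Figure 1 | Stated | Ratio |
|---|---|---|---|---|
| Intervention | 20 | 1480 | 2960 | 2.0 |
| Control | 20 | 1480 | 2960 (5920 − 2960) | 2.0 |
| Overall | 40 | 2960 | 5920 | 2.0 |

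Without rounding 73.75 up, the overall figure is 2950, so rounding explains nothing.

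**5. What the stated totals would need.** Within Figure 1 they require 2960 / 20 = 148, or equally 5920 / 40 = 148, patients per hospital-period. That is twice the plan's average and close to the top of the range of 30 to 158 that Section 5.2.3 reports from preliminary data. At 148 per equal-sized cell, power would be about 0.99.

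**The case against.** The best defence is that 5920 includes historical controls. Section 4.2 plans to pull historical records by ICD-10 code, Section 1.3 says that "Demographics and comorbid conditions will be characterized among the historical population of patients at CHS with COPD exacerbation", and the sentence with 5920 speaks of including the control population. If the intervention group loosely meant the stepped-wedge cohort, 2960 would be the trial and the other 2960 a historical pool. Such a pool would equal 2960 / (8 × 74) = 5 two-month periods, or ten months at all eight hospitals. The documents cannot exclude that this is what was meant, so the claim that 5920 arose by doubling the design is an inference, though the doubling is exact. But no section gives the size, dates or role of such a pool, and neither Figure 1 nor the primary model in Section 5.2.5 contains one. It would also add no intervention patients, so the label on 2960 stays wrong.

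A second point is that 1480 is an expected value. Hospitals differ in volume, and the intervention share depends on which cross early. With assumed hospital volumes per two months of 30, 45, 55, 60, 70, 82, 92 and 158 (mean 74, coefficient of variation about 0.5), the intervention total runs from 1199 to 1761 of 2960, depending on the order. This is a fair reason to write *about 1480*; no order in that example comes near 2960.

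Third, the consequences are modest: Section 4.1 disclaims an accrual target, and no stopping or analysis rule in the text uses either total. That is correct, and it bounds the harm. It does not make the totals right.

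**Conclusion.** The concern holds. On the plan's own cell size and Figure 1, the trial comprises 2960 patients overall, about 1480 in each condition. The intervention figure (synopsis and Section 5.2.3) and the overall figure (Section 5.2.3 only) are each overstated by a factor of two. This rests on the five periods and eight hospitals of Figure 1 and on the required average of 74; the equal split also assumes that hospital volume is unrelated to crossover order, which randomization gives in expectation.

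The cell sizes of 59 and 74 reproduce, and a trial of 2960 in all is not underpowered on the plan's inputs: 74 per equal-sized cell gives about 0.86 to 0.91 before any loss from unequal cluster sizes. The error lies in the stated totals and their labels.

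**What to change.** First establish whether 5920 was meant to count anything outside Figure 1. Then:

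- In Section 5.2.3, replace the end of the sentence with text such as: *an average of 74 patients per hospital-period, giving 2960 patients in all (8 hospitals × 5 periods × 74), about 1480 in intervention periods and about 1480 in control periods*. Delete 5920.
- In the synopsis, make the same correction to the description of 2960.
- If historical control records were intended, list them on a separate line with their source, dates, expected number and analytic role, and state that they are not part of the power calculation.

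The cost is two sentences. Design, data collection, analysis and power stay as they are; the stated planned size halves.

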5.2.4 Statistical analysis

All data quality monitoring and analysis will be overseen by [name]. Distributions of baseline characteristics for hospitals and patients will be compared between the intervention or control periods to assess effectiveness of the randomization, and statistical or clinical differences will be adjusted in sensitivity analyses. All analyses for treatment and control periods comparisons will use an intention-to-treat approach and results will be reported using the CONSORT extension to cluster randomized trials.

5.2.5 Primary aim

The primary outcome for this study is 60-day non-elective acute care utilization. Characteristics of the hospitals and individuals will be summarized by levels of randomization steps, hospitals and individuals. The count, rates and 95% confidence intervals of 60-day non-elective acute care utilization in the -control period will be presented and compared with that in the -treatment period. The primary analysis will be conducted using generalized estimating equations with fixed effects for intervention, time (steps), and intervention multiply by the time, accounting for the cluster randomized trial design with a random cluster (hospitals) effect. We will estimate and report the intra class correlation coefficients for all outcome measures to assess assumptions for sample size analyses and for future investigations using similar designs and outcomes. The primary analyses will follow the intention to treat principle with an additional per protocol analysis including by using denominator in those who had pathway ordered as well as intervention periods when truly occurred. The secondary analyses will include within cluster comparisons of intervention and control periods (not adjusting for any confounding effect of time), as well as comparisons of a series of (unbalanced) quasi-parallel cluster trials between those enrolled and unenrolled clusters at each intervention enrollment period. The same analyses plan will also be applied to secondary outcomes.

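### The primary model includes an intervention-by-time term, but the plan does not say which coefficient or contrast is the single primary odds ratio

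*Combined protocol and SAP*

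**What the plan says.** Section 5.2.5 describes the primary analysis as "generalized estimating equations with fixed effects for intervention, time (steps), and intervention multiply by the time", and the same sentence adds that clustering is handled "with a random cluster (hospitals) effect". It does not say whether time is categorical or continuous, where its origin or reference lies, or which coefficient, average or joint test is the primary result.

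The rest of the plan speaks of one comparison:

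- Section 1.1 hypothesises lower 60-day utilization under the pathway than under usual care.
- The synopsis (Statistical Analysis) compares two groups of patients by GEE with a logit link and reports odds ratios with 95% confidence intervals. It mentions no time term, interaction or random effect.
- Section 5.2.3 sizes the trial for one change, "from 43% in the control period to 33% in the intervention period".
- Section 5.2.5 also says that rates "in the -control period will be presented and compared with that in the -treatment period". This names the two conditions but not how the model compares them.

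On the layout, Section 5.2.2 says "The stepped wedge design implies a baseline period, in which no clusters are exposed to the intervention". The last row of Figure 1, "Cluster 8 | 0 | 0 | 0 | 0 | 1", shows that by the fifth period every hospital has crossed over. Section 5.2.5 ends with "The same analyses plan will also be applied to secondary outcomes".

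**The concern.** Once an intervention-by-time product is in the model, the coefficient labelled intervention is no longer an overall effect. It is the effect at the reference period or time origin. Someone must then choose a coding, a reference period or a pooled contrast. Several choices are defensible, and they can give different odds ratios and confidence intervals. If the choice is not fixed in the plan, it may be made after the data have been seen. At stake are the primary result and, through the closing sentence of Section 5.2.5, the secondary outcomes.

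A related ambiguity sits in the same sentence. With a logit link, GEE gives a population-averaged odds ratio and a random-hospital-effect model gives a hospital-conditional one. Naming both leaves the reported quantity open in a second way.

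**Working it through.** **Inputs.** From Figure 1: 8 hospitals, 5 periods, two hospitals crossing at each step. From Section 5.2.3: 43% versus 33%, ICC 0.05, two-sided α 0.05, 59 per hospital per two months (74 after inflation). Assumed, because the plan does not give the PASS model: risk-difference scale, total variance 0.43 × 0.57 = 0.2451, equal cells, exchangeable correlation, normal approximation.

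**Step 1: reproduce the plan's 59.** Take the standard stepped-wedge variance for one constant effect with categorical periods and no interaction:

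Var = Iσ²(σ² + Tτ²) / [(IU − W)σ² + (U² + ITU − TW − IV)τ²]

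- I = 8, T = 5.
- U = 20 intervention cells.
- W = 0 + 4 + 16 + 36 + 64 = 120 (squared numbers of intervention hospitals per period).
- V = 2(16 + 9 + 4 + 1) = 60 (squared numbers of intervention periods per hospital).
- τ² = 0.05 × 0.2451 = 0.012255; σ² = 0.95 × 0.2451 / 59 = 0.003947.
- IU − W = 40; U² + ITU − TW − IV = 400 + 800 − 600 − 480 = 120.
- Var = 8 × 0.003947 × 0.06522 / (0.1579 + 1.4706) = 0.001264, so SE = 0.0356.
- Power = Φ(0.10/0.0356 − 1.96) = 80.3%, and 59 is the smallest size that reaches 80%. At 74 the power is 88.1%.

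Other variance conventions give 53 to 62 per cell. The stated 59 is therefore consistent with a constant-effect model.

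**Step 2: categorical steps with interaction.** The model has 10 columns: five period indicators and five intervention-by-period indicators (equivalently an intercept, four periods, intervention and four products). In period 1 no hospital is on intervention, so that intervention column is all zeros. In period 5 every hospital is, so that column equals the period 5 indicator. Two columns are redundant and the rank is 8. The period 2, 3 and 4 effects are estimable; the period 1 and 5 effects are not. The intervention coefficient is thus not estimable with period 1 or 5 as reference, and otherwise is the reference period's effect:

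| Reference period | SE at 59 | Power for 10 points |
|---|---|---|
| 1 or 5 | not estimable | – |
| 2 | 0.0577 | 41% |
| 3 | 0.0503 | 51% |
| 4 | 0.0577 | 41% |

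**Step 3: linear interaction.** The model is now estimable, but the intervention coefficient is the effect at time zero. SE and power at 59:

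| Time coding | Categorical period main effects | Linear main effect |
|---|---|---|
| 1 to 5 | 0.1217, 12.8% | 0.0704, 29.5% |
| 0 to 4 | 0.0853, 21.5% | 0.0539, 45.8% |
| Centred at period 3 | 0.0356, 80.3% | 0.0356, 80.3% |

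**Step 4: pooled contrast.** Weighting the period 2, 3 and 4 effects by 0.3, 0.4 and 0.3 gives SE 0.0356 and power 80.3% at 59 (88.1% at 74). With equal cells on the risk-difference scale this is the same estimator as in Step 1. Equal thirds give 79.8% at 59.

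**Step 5: sensitivity to the layout.** Section 5.2.3 also gives 5920 patients overall, and 5920 / 74 = 80 cells against Figure 1's 40. Assuming the other 40 are five further all-control periods, constant-effect power at 59 becomes 89%. Estimability does not change: only the three periods with both conditions inform the effect, again with weights 0.3/0.4/0.3.

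**The case against.** The strongest reply is that the comparison is not in doubt. The plan names intervention versus usual care, a logit link, and an odds ratio with its interval. A competent statistician would pool the estimable effects or drop the interaction, and either way the planned power is kept. Section 5.2.5 also lists further analyses, including "comparisons of a series of (unbalanced) quasi-parallel cluster trials between those enrolled and unenrolled clusters at each intervention enrollment period".

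Much of this stands. The comparison is named and the power can be kept. But naming two conditions does not define an estimator when the model carries a separate effect for each period, and the further analyses are labelled secondary. The choice belongs in the plan.

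Three stronger readings are tempting, and the documents do not support them.

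- A reader might infer that the model yields no odds ratio at all. That goes too far: three period effects, their pooled contrasts and a centred linear-time effect are all estimable. What is missing is the statement of which one is primary.
- A reader might take the 13–51% figures as evidence of an underpowered trial. They are powers of raw coefficients that the plan never names as its result.
- A reader might conclude that the sample size was calculated without an interaction. The match at 59 shows consistency only, because the plan names the software but not the model.

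Nor are categorical and linear calendar time the only readings. The product term could be meant as time since crossover, which is estimable. That adds to the ambiguity.

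**Conclusion.** The point holds as a specification fault in the primary analysis. The model in Section 5.2.5 does not by itself return the one odds ratio on which the hypothesis, synopsis and sample size rely. The rank result (8 of 10) and the dependence on time origin follow from the model's terms and Figure 1 alone.

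The power figures are conditional on 40 equal cells of 59, ICC 0.05, total variance 0.43 × 0.57, the risk-difference scale and exchangeable correlation, with no small-sample correction. On those terms the raw intervention coefficient has 41–51% power (categorical) or 13–80% (linear, by coding), against 80.3% for the constant-effect model or the pooled contrast. The trial's planned power is not refuted. What is at risk is an undeclared choice of the primary estimate. Small-sample inference with 8 hospitals is a separate question and carries no weight here.

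**What to change.** In Section 5.2.5, make the primary model logit link with intervention (0/1) plus five-level categorical period and no interaction. Name its intervention odds ratio and 95% confidence interval as the primary result, and list intervention by time as a secondary analysis. State the same model in the synopsis. An alternative is to keep the interaction and pre-specify one pooled contrast, for example exp(0.3 b2 + 0.4 b3 + 0.3 b4), where b2 to b4 are the period 2 to 4 log odds ratios. In the same sentence, name either GEE or a random-hospital-effect model, not both.

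The cost is a few sentences, and the planned power is unaffected by the choice of contrast. One downside should be stated in the plan. The estimate draws on the periods in which both conditions are present, and it is not an ordinary average if the effect changes with time since crossover. On the 40-cell layout at 59 per cell, the weights on the first to fourth exposure periods are 0.96, 0.30, −0.08 and −0.18. For example, an effect growing 4, 8, 12, 16 points averages (8×4 + 6×8 + 4×12 + 2×16)/20 = 8 points over the 20 intervention cells. It would be estimated as 0.96×4 + 0.30×8 − 0.08×12 − 0.18×16 = 2.4 points. With five added control periods the weights are 0.74, 0.30, 0.03 and −0.07, and the estimate is about 4.6 points.

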| Study Procedures | 
During this project, patients who are hospitalized at select CHS sites with COPD acute exacerbation symptoms will be treated per the CHS COPD clinical pathway (COPD Pathway). The COPD clinical pathway will include four components: (i) discrete, evidence-based care steps (ii) patient navigation, (iii) daily data driven care gap identification, (iv) monthly leadership huddles.
 
The evidence based care steps include: (1) verification of COPD diagnosis and severity, (2) patient/caregiver education regarding COPD and basic self-management skills, (3) standard pharmacologic bundle of systemic steroids, empiric antibiotics, bronchodilators, (4) pneumococcal and influenza vaccination review and completion, (5) smoking cessation advice and therapy when appropriate, (6) comprehensive care management assessment, (7) recommendations for pulmonary consultation, (8) recommendations for palliative care consultation, (9) use of discharge checklist, (10) recommendations for content of outpatient follow-up, and will be driven primarily by provider utilization of a comprehensive order-set that includes each component and a discharge checklist.
 
Patient navigation will be provided by the COPD Pathway Coordinator (COPD Coordinator) at each site. This role will be filled by an individual (s) who already exists on a site's care team. Because of this, the COPD Coordinator's site role and background may vary by site. The COPD Coordinators will be responsible for daily monitoring of care gaps that exist for COPD patients and their respective sites and alerting appropriate team member to help close those gaps. The COPD Coordinators will receive a daily COPD Gaps list. The COPD Gaps list identifies patients who are hospitalized at that time and the associated gaps in receiving the evidence based care components.
 
The intervention occurs at the site level and sites are randomized to the order they will receive the intervention in clusters of two. Two additional facilities will be added on a rolling basis in 2 month intervals, until all 8 facilities are active in using the COPD pathway. Once added, sites will begin utilizing the COPD Pathway in their daily practice.
 
As a part of the COPD clinical pathway, patients will meet the following discharge checklist criteria:
 
• On a long acting bronchodilator for 24 hours• A short acting bronchodilator is scheduled no more frequently than 4 times daily for 24 hours |

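### Section 5.2.5 lets the pathway effect vary with calendar step but not with time since each hospital's go-live, so an effect that builds up could be understated in the primary estimate.

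*Combined protocol and SAP*

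**What the plan says.** Section 5.2.5 defines the primary analysis as "generalized estimating equations with fixed effects for intervention, time (steps), and intervention multiply by the time". On the handling of hospitals, the same sentence describes the model as "accounting for the cluster randomized trial design with a random cluster (hospitals) effect". The synopsis (Statistical Analysis) adds that the comparison is made "using a logit link in the generalized estimating equations" and that "Results will be presented with odds ratios and 95% confidence intervals". Neither place says whether step is categorical or linear, which working correlation is used, or which contrast is the primary estimate once the interaction is in the model.

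Figure 1 in section 5.2.2 codes each hospital-period as "0=control 1=intervention", with two hospitals crossing at each two-month step. The sample size in section 5.2.3 rests on one change in rates, "from 43% in the control period to 33% in the intervention period". No section has a term for time since a hospital's own go-live, and no start-up period is left out of the intention-to-treat analysis.

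Three other passages matter. The synopsis (Study Procedures) gives the coordinator role to existing staff whose "site role and background may vary by site", and includes monthly leadership huddles. Section 5.3 starts training two to three weeks before the first patient. Section 5.2.5 also lists secondary comparisons of enrolled with unenrolled hospitals at each enrollment period, and a per-protocol analysis.

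**The concern.** A pathway run by staff in a new role, trained shortly beforehand and steered by monthly meetings may take some months to reach its full effect. The relevant clock would then be time since go-live. The four hospital pairs reach the same exposure at different calendar steps: at the last step in Figure 1 the hospitals have between one and four periods of exposure. An interaction with calendar step cannot separate these.

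Once step effects are in the model, hospitals already on the pathway also serve as comparators for those that cross later. If their effect is still growing, part of that growth is absorbed into the step effects and subtracted from the pathway effect. The trial is meant to tell the health system whether the pathway changes utilization. An understated effect would bear directly on that decision, and an exposure-time analysis added after a null result would look post hoc.

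**Working it through.** **Inputs from the documents.** 8 hospitals, 5 periods, two crossing per step (Figure 1); 43% and 33%, ICC 0.05, 59 per hospital per two months, two-sided alpha 0.05 (section 5.2.3).

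**Assumed.** The effect profiles by time since go-live, equal cell sizes, and an exchangeable correlation equal to the ICC.

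**1. The plan's own figure.** Take the standard stepped-wedge variance (step fixed effects, random hospital effect) with the mean binomial variance (0.43×0.57 + 0.33×0.67)/2 = 0.2331 as the within-hospital variance. At 59 per cell, power is 0.8025. The stated 59 and 0.80 are reproduced for a constant effect.

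**2. What a single-effect estimate averages.** Use generalized least squares with total variance 0.38×0.62 = 0.2356 and covariance of hospital-period means 0.2356×[(0.95/59)I + 0.05J]. The standard error of the single effect is 0.0349, so power for a constant 10 points is Φ(0.10/0.0349 − 1.96) = 0.82. Summing the estimator's coefficients over hospital-periods with the same exposure gives the weights. Figure 1 has 8, 6, 4 and 2 hospital-periods at the four exposures, out of 20.

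| Months since go-live | 1-2 | 3-4 | 5-6 | 7-8 |
|---|---|---|---|---|
| Weight, correlation 0.05 | 0.961 | 0.300 | -0.081 | -0.181 |
| Weight, working independence | 0.60 | 0.30 | 0.10 | 0.00 |
| Patient share | 0.40 | 0.30 | 0.20 | 0.10 |

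At 74 per cell the first row is 0.968, 0.300, -0.084 and -0.184.

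**3. Assumed profiles (percentage-point reduction), correlation 0.05.**
- 8/9/10/10: estimate 0.961×8 + 0.300×9 − 0.081×10 − 0.181×10 = 7.8; mean 0.4×8 + 0.3×9 + 0.2×10 + 0.1×10 = 8.9. Shortfall 1.1/8.9 = 12%.
- 5/10/10/10: estimate 4.805 + 3.000 − 0.810 − 1.810 = 5.2; mean 8.0. Shortfall 2.8/8.0 = 35%.
- 2.5/5/7.5/10: estimate 2.403 + 1.500 − 0.608 − 1.810 = 1.5; mean 5.0. Shortfall 3.5/5.0 = 70%.

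**4. With the planned interaction.** If step is categorical, the interaction can be estimated only at steps 2 to 4, because all hospitals are control at step 1 and all are treated at step 5. For the last profile these effects are -0.3, 1.5 and 3.3, averaging 1.5, the same as the single effect. If step is linear and the effect is averaged over treated hospital-periods, the results are 3.3 against 5.0 (last profile) and 7.1 against 8.0 (second).

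**5. Working independence, single effect.** The last profile gives 0.60×2.5 + 0.30×5 + 0.10×7.5 = 3.75 against 5.0.

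**6. Logit scale.** The plan's full effect is an odds ratio of (0.33/0.67)/(0.43/0.57) = 0.653. Let the log odds ratio reach it in quarters (25, 50, 75, 100%), with correlation 0.05. The expected single-effect odds ratio is then 0.937, against 0.808 averaged over treated hospital-periods (shortfall 69%). With the mild curve (80, 90, 100, 100%) it is 0.717 against 0.684 (12%). Unequal sizes from 30 to 158 (mean 74) move the 0.937 only between 0.926 and 0.950 across random orders.

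**7. Precision of the alternative.** All four exposure effects are estimable in Figure 1. The standard error of their patient-weighted average is 0.0458 at 59 per cell, against 0.0349.

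**The case against.** The strongest reply is that nothing in the documents says how fast the effect builds. Section 9 says the care components are already in use in the system's facilities, and training precedes the first patient. That stands: the profiles above are illustrations, and under the mild one the loss is about one point in nine.

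The size also depends on choices that the plan leaves open. Under working independence no exposure gets a negative weight. With independence and a linear interaction averaged over treated periods, the shortfall can vanish (odds ratio 0.809 against 0.808 for the steady rise) or reverse (0.692 against 0.711 when half the effect is present in the first two months). That stands too. The random-hospital wording suggests an exchangeable structure, but the plan does not state the working correlation.

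The enrolled-versus-unenrolled comparisons in section 5.2.5 use only not-yet-enrolled hospitals as controls. Under the steady rise their expected values at steps 2 to 4 are 2.5, (5 + 2.5)/2 = 3.75 and (7.5 + 5 + 2.5)/3 = 5.0, so they could show the growth. They are nonetheless secondary, and they do not index exposure time.

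A reader might also infer that this bias takes power from 0.82 to 0.32 or 0.07 under the second and third profiles. That does not follow. The 0.82 is for a constant 10 points, while those profiles average 8.0 and 5.0. An unbiased estimator with the same standard error would have power of only Φ(8.0/3.49 − 1.96) = 0.63 and Φ(5.0/3.49 − 1.96) = 0.30. Part of the first drop, and most of the second, is simply a smaller true effect.

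**Conclusion.** The gap is real. The primary model has no term for time since go-live, and the calendar-step interaction is not a substitute. If the effect builds, a single-effect or step-averaged estimate could be biased toward no effect. With exchangeable correlation 0.05 and 59 per cell, the shortfall is about 12% for a mild build-up, 35% if half the effect is present in the first two months, and 70% for a steady rise over eight months. The weights follow from Figure 1, the model and the correlation; the profiles are assumptions.

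It is tempting to conclude that the primary result will be strongly biased, or that a working pathway would be reported as ineffective. The documents do not support that. They give no evidence on the speed of uptake, leave the working correlation and the primary contrast open, and already plan comparisons that could reveal a rise. The supportable statement is that the estimate could understate the effect, substantially if uptake is slow.

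**What to change.** In section 5.2.5, pre-specify a sensitivity analysis that keeps calendar step as a main effect and replaces the intervention-by-step term with categories of time since go-live (months 1-2, 3-4, 5-6, 7-8). Report the four effects and their patient-weighted average, with confidence intervals, beside the primary odds ratio. State in advance that, if the effects rise with exposure, the primary odds ratio will be described as possibly understating the pathway's effect.

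Keep the primary test unchanged, and do not make its reading conditional on agreement between the two estimates. The standard error of their difference is about √(4.58² − 3.49²) = 3.0 points. Gaps of 2.8 or 3.5 points, as in the second and third profiles, are about one standard error, so such a rule would often miss real bias or flag chance.

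The cost is SAP wording and one extra model, with no new data. The exposure-time average is less precise (about 4.6 against 3.5 points at 59 per cell), which is why it should accompany the primary analysis and not replace it.
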